10. STUDY DESIGN

Study Type

Interventional

Study Design

International multicentre, prospective, randomised, double blind (subjects, investigators and outcomes assessors), active control, parallel assessment, intention to treat, safety and efficacy study.

Primary endpoint

One-year all-cause mortality

Secondary endpoints

1. MI: Defined by any of

a) A typical rise of troponin OR a typical fall of an elevated troponin OR a rapid rise and fall of CK-MB, PLUS one of the following: i) ischaemic symptoms, ii) pathological Q waves, iii) ECG changes indicative of ischaemia, iv) coronary artery intervention, and/or v) new or presumed new wall motion abnormality on echo or mibi scan; OR b) Autopsy findings of MI.

- 2. **Cardiac arrest:** Defined as a successful resuscitation from either documented or presumed ventricular fibrillation or sustained ventricular tachycardia or asystole.
- 3. **Pulmonary embolism:** high probability VQ scan or documented on pulmonary angiogram or spiral CT, or at autopsy.
- 4. **Stroke:** cerebral infarction or haemorrhage on CT or MRI scan, or new neurological signs (paralysis, weakness or speech difficulties) lasting more than 24 hours or leading to earlier death.
- Sepsis: Surviving Sepsis Campaign definitions with backdating of data. [62] (Previously Centers for Disease Control and Prevention with National Healthcare Safety Network criteria [53]: - SIRS plus infection (positive blood culture or purulence from any site). This change means a clearer distinction between systemic inflammatory response syndrome and sepsis.
- 6. **Surgical site infection:** if associated with purulent discharge and/or a positive microbial culture.
- 7. ICU stay: including initial ICU admission and readmission time.
- 8. Hospital stay: from the start (date, time) of surgery until actual hospital discharge.
- 9. Awareness: Questioning for evidence of awareness under anaesthetic using the modified Brice questionnaire administered once, preferably on the day following surgery and again on day 30 [50,54,55]. This consists of four questions:

1. What is the last thing you remember happening before you went to sleep?

- 2. What is the first thing you remember happening on waking?
- 3. Do you remember anything in between?
- 4. Did you have any dreams while you were asleep?

Affirmative responses will trigger a more detailed interview and counselling as required for the patient should there have been frank awareness.

- 10. WHODAS score: pre-operative, day 30 and 1 year
- 11. **Disability free survival**: disability-free survival up to 1 year: survival and freedom from new-onset disability, the latter defined as a 4-point reduction in the WHODAS score [56]. Disability in the WHODAS score is self reported by the participant, if the participant is unable to complete the score, then we will use a proxy's report as per WHODAS standard procedures. The date of onset of new disability will be recorded.
- 12. **Persistent post-operative pain**: pain over the surgical site, for at least three months after surgery, that cannot be explained by other causes, such as disease recurrence or a pre-existing pain syndrome.
- 13. **Cancer recurrence:** defined as clinical radiological or pathological evidence for recurrence of the tumour either at the local or a distant site.

Inclusion criteria

Age ≥ 60 years, ASA physical status 3 or 4, surgery expected to last ≥ 2 hours, post-operative hospital stay expected to be ≥ 2 nights, general anaesthesia with or without major regional block, able to monitor BIS throughout anaesthesia.

Exclusion criteria

Unable to monitor BIS (e.g. cranial or intracranial surgery), unable to consent, surgery with 'wake-up' test, propofol infusion for part or all of maintenance of anaesthesia ('total intravenous anaesthesia'), previous enrolment in Balanced study.

Intervention

General anaesthesia monitored with BIS. BIS targets will be either 50 or 35. We expect 90% of anaesthesia time to be within 5 units of the target BIS value and no deviations for >5 minutes.

Consent

Patients who are eligible for the trial will be given the patient information sheet by a member of the research team and encouraged to discuss the study with their family (or family/whanau in New Zealand) before written informed consent is sought, in accordance with local practice.

Treatment allocation

Once all entry details are recorded and eligibility confirmed, randomisation will be performed by contacting the automated on-line randomisation service with back-up phone service. Assignment to one of the two groups will be stratified by collaborating centre and a unique study number assigned. Investigators and research staff involved in patient followup are blinded to treatment allocation.

Perioperative Care

Anaesthesia will consist of standard anaesthetic hypnotics, volatiles, opioids and relaxants, intravenous or inhalational induction, volatile maintenance, opioids and muscle relaxants, with continuous BIS monitoring. No use of nitrous oxide will be allowed due to its interference with accurate BIS readings and similarly no infusions of ketamine above 25 mg/h will be allowed.

An individualised mean arterial blood pressure target range appropriate for the patient being studied will be set by the anaesthetist before BIS target randomisation. Anaesthetists will be encouraged to maintain patient normothermia and to give DVT prophylaxis and antibiotic prophylaxis as per local institutional practice. Other aspects of anaesthesia and perioperative care will be at the discretion of the anaesthetist. All complications (including those defined as secondary outcomes) will be managed according to routine institutional practice.

Recordings

Data will be collected by interviewing patients, relatives and doctors, and by review of hospital medical records and national databases (if applicable). Source documentation may be requested for any or all data recorded. Any or all data recorded may be subject to assessment by the Endpoint Adjudication Committee (on the direction of the Steering Committee).

Pre-operative

Age, sex, height, weight, ASA physical status, electrocardiogram (ECG), haemoglobin, creatinine, albumin, updated Charlson co-morbidity score [57,63], WHODAS-12 score

Intra-operative

Electronic *or* printed record with minimum of 5 minutely recording of BIS, burst suppression ratio (SR), end-tidal volatile anaesthetic concentration, mean arterial blood pressure and heart rate.

Manual record of all drugs used, including total dose of opioids used and regional or local anaesthetic blocks used.

Recovery

Analgesic and antiemetic requirements, time of arrival and eligibility for discharge.

Post-operative days 1, 2, 3

Routine laboratory testing.

Incidence of MI, cardiac arrest, PE, stroke, sepsis, surgical site infection and other adverse events.

Questioning for evidence of awareness under anaesthesia using the modified Brice questionnaire administered once, preferably on the day following surgery.

Analgesic and antiemetic requirements.

Quality of recovery: A validated post-operative quality of recovery score, the QoR-15 score will be recorded [58].

Post-operative day of discharge Length of hospital stay, unanticipated ICU admission, ICU stay, unplanned second operation

Post-operative day 30

Survival, ongoing analgesic or antiemetic requirements. Incidence of MI, cardiac arrest, PE, stroke, sepsis, surgical site infection, awareness, QoR-15, WHODAS score, persistent post-operative pain and other adverse events, staging of cancer (in cancer patients).

Post-operative one year

Survival. Disability free survival.

Incidence of MI, cardiac arrest, PE, stroke, sepsis, surgical site infection, WHODAS score, persistent post-operative pain (using modified pain inventory and neuropathic pain questionnaire if there is pain present [59,60])

In cancer patients, definitive Tumour-Node-Metastasis staging of cancer and evidence of any recurrence

All these measures are in frequent use and have been validated in past studies both of anaesthetic outcome as already discussed and in the general medical literature. Definitions of outcomes will be those used in the current ENIGMA-II Trial (a study of the influence of nitrous oxide on long term outcome from anaesthesia) and RELIEF trial [61] (see appendix).

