been published using available databases. Five of these have found similar increases in mortality. In Lindholm et al.'s study, deep hypnotic time was not a predictor when pre-existing malignancy was included in the model. If deep hypnotic time was >2 hours subsequent mortality was much higher. Searleman et al.'s study found that non-surviving patients received slightly less volatile anaesthetic than the survivors, implying that patients who died may have been sensitive to the anaesthetic drugs. Saager et al.'s study used a very large database with 24,000 patients, and found three independent predictors of increased one year mortality, which were minimum alveolar concentration (MAC) <0.4, mean arterial pressure (MAP) <80 mmHg and BIS<40. (MAC is a normalised measure of anaesthetic potency). The risk to those who received deep anaesthesia was again a 20% increase in one-year mortality. Patients with a low MAP during the procedure faired even worse, and the combination of all three factors was associated with a RR=1.6 for one year mortality. They also found that patients who had an instance of low MAP, which was treated within 5 minutes had improved outcomes, indicating that although patients who were sensitive to anesthesia did poorly, early intervention was effective. Leslie et al analysed long-term outcomes in the B-Aware Trial, a 2,500 patient trial conducted principally in New Zealand, Australia and Hong Kong. This study also found an increased risk of myocardial infarction and cerebrovascular accident in the deep anaesthesia group. There were a large number of cardiac patients in the study and the same relationship of depth with poor outcome was confirmed, a finding repeated by Kertai et al. [17].

Author	Ν	ASA	1 y	Increased risk of
		3&4 *	mortality	death if 'deep' [#]
Monk 2005 [12]	1064	35%	5.5	RR = 1.24
Lindholm 2009 [13]	4087	6%	4.3	HR = 1.18
Saager 2009 [14]	23,999	~30%	4.8	RR = 1.63
Searleman 2010 [15]	1791	71%	10.7	OR = 1.25/h
Leslie 2010 [16]	2463	74%	10.8	PS = 1.42 (at 4y)
Kertai 2010 (cardiac) [17]	460	100%	17.8	HR = 1.29 (at 3y)
Kertai 2011 (non-cardiac) [18]	1473	60%	24.3	HR = 1.03 (at 3y)

TABLE 1 Observational studies of the relationship between depth of anaesthesia and subsequent mortality

*ASA=American Society of Anaesthesiologists physical status scale, 1=normal health, 2=mild to moderate systemic disturbance, 3=severe systemic disturbance which limits activity, 4=incapacitating life threatening disease, 5=moribund.

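### The MI definition accepts any coronary artery intervention and coronary surgery is not excluded, so an enrolled bypass patient with a recorded biomarker change can meet the MI endpoint through the index operation

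*Protocol*

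**What the plan says.** Protocol section 10 (Secondary endpoints, item 1) defines MI by autopsy or by a biomarker limb plus a supporting feature. The biomarker limb is "A typical rise of troponin OR a typical fall of an elevated troponin OR a rapid rise and fall of CK-MB, PLUS one of the" five features listed after it. The first three are ischaemic symptoms, Q waves and ischaemic ECG changes. The last two are "iv) coronary artery intervention, and/or v) new or presumed new wall motion abnormality on echo or mibi scan". Feature v must be new or presumed new. Feature iv carries no qualifier. No biomarker threshold is set, and cardiac surgery has no rule of its own.

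The inclusion criteria in the same section set an age limit and ask for "ASA physical status 3 or 4, surgery expected to last ≥ 2 hours, post-operative hospital stay expected to be ≥ 2 nights", general anaesthesia and BIS monitoring. They do not restrict the type of operation. The exclusions begin "Unable to monitor BIS (e.g. cranial or intracranial surgery), unable to consent, surgery with 'wake-up' test, propofol infusion for part or all of maintenance" and end with previous enrolment. Cardiac and coronary surgery are not among them.

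Section 10 (Recordings) also says: "Definitions of outcomes will be those used in the current ENIGMA-II Trial" and in a second named trial, and it points to an appendix. On postoperative days 1 to 3 it schedules "Routine laboratory testing" and does not name troponin.

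MI is used in three places. It is a secondary hypothesis at 30 days and one year (section 8), a component of the four-part composite (sections 8 and 13), and a candidate predictor in the Cox model of one-year mortality (section 13).

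**The concern.** A supporting feature in an MI definition is meant to show that a biomarker change reflects an ischaemic event. In a patient whose index operation is a coronary bypass graft, a bare reference to coronary intervention is satisfied before any complication has occurred. If a troponin or CK-MB change of the required kind is then recorded, the definition is met on its face.

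Events produced this way are set by the type of operation, not by anaesthetic depth. They would raise the MI and composite rates in both arms, pull the risk ratio towards 1, and make the reported MI rate hard to read as a complication rate. In the Cox model, MI would partly stand for type of surgery.

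**Working it through.** **Reading the text.** Four questions decide whether the literal reading is open.

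1. Does feature iv exclude the index operation? No. It has no condition on timing, indication or procedure.
2. Is a bypass patient eligible? As written, yes, if aged 60 or over, ASA 3 or 4, with volatile maintenance and BIS monitoring. The exclusions do screen by operation (cranial surgery, wake-up test) but do not name cardiac surgery. The hypotheses in section 8 speak of major surgery without restricting it to non-cardiac.
3. Does the appendix narrow the definition? No. Section 23 and the table of contents list scores, questionnaires and a flow chart, and no outcome definitions.
4. Does adjudication discount the index operation? No stated rule does so. Section 17 gives blinded review at the Steering Committee's direction plus a random 10% of outcome events.

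**The plan's own figure.** The only sample size stated is for mortality: p1 = 0.10, p2 = 0.08, α = 0.049, 80% power, 3,250 per arm.

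n = [z(1−α/2)·√(2p̄q̄) + z(0.80)·√(p1q1 + p2q2)]² / (p1 − p2)²

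With p̄ = 0.09 this is [1.969·√0.1638 + 0.842·√0.1636]² / 0.02² = 3,233. Power at 3,250 per arm is 80.2%. The figure reproduces, and this point does not touch it.

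**Size for MI, by assumption.** None of the following is in the protocol: an MI rate of 5% (deep) v 4% (light), so a true risk ratio of 0.80; two-sided α of 0.05; and a share c of each arm having bypass surgery, all counted as MI. The arm size of 3,250 is the protocol's. The observed rate in an arm is

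p′ = c + (1 − c)·p

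For c = 5%: deep 0.05 + 0.95 × 0.05 = 9.75%; light 0.05 + 0.95 × 0.04 = 8.80%; risk ratio 0.903; share of deep-arm MIs due to the index operation 0.05 / 0.0975 = 51%.

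| Bypass share (of 6,500) | Deep v light | Risk ratio | Power | Deep-arm MIs from index operation |
|---|---|---|---|---|
| 0% | 5.00% v 4.00% | 0.80 | 49% | 0% |
| 1% (65) | 5.95% v 4.96% | 0.83 | 42% | 17% |
| 5% (325) | 9.75% v 8.80% | 0.90 | 26% | 51% |
| 10% (650) | 14.5% v 13.6% | 0.94 | 18% | 69% |

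Power uses the two-proportion normal approximation with pooled variance under the null.

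**Sensitivity.** At a 5% bypass share the risk ratio is 0.93 if the deep-arm MI rate is 3%, and 0.88 if it is 8%. If only a fraction g of bypass patients has a qualifying change recorded and the rest follow the assumed MI rates, c is replaced by c·g. A 5% share with one in five recorded gives the 1% row (0.05 × 0.2 = 0.01).

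**The case against.** **An ordinary reading avoids the problem.** Section 10 (Perioperative Care) treats the secondary outcomes as complications, and an operation is not its own complication. A site or adjudicator might also take the phrase to mean a later or catheter-based procedure. That is a sensible reading, but the text does not require it. An endpoint that depends on which reading each site adopts is not well fixed.

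**Other machinery may settle it.** The Steering Committee decides definitions, events can be sent for blinded adjudication, and the definitions are said to follow two other trials. Those definitions are not reproduced, so it cannot be known whether they set the index operation aside. What sites have in front of them is section 10.

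**Few bypass patients may be enrolled.** Section 14 expects the patient pool to overlap with ENIGMA-2 and POISE-2. It does not mention the coronary surgery trial that section 9 lists for the same group. Propofol infusion for any part of maintenance is an exclusion, and the flow chart assumes a recovery-room record. These points suggest that the share may be small or nil. They are not an exclusion.

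**The stakes are modest.** MI is not a powered comparison: under the assumptions above its power is only 49% before any dilution. At a 5% share the absolute difference moves only from 1.00 to 0.95 percentage points. The effect is about equal by arm and creates no false-positive bias. All of this stands, and it limits the weight of the point.

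**Stronger readings that the documents do not support.**

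- A reader might infer that all bypass patients would be counted as MI. The biomarker limb must be met first, troponin is not a scheduled test, and the protocol does not say that a qualifying change follows each such operation.
- A reader might extend the point to cardiac arrest, through planned arrest on bypass. Endpoint 2 requires successful resuscitation, which does not plainly describe a planned arrest.
- A reader might take the Background remark "There were a large number of cardiac patients in the study and the same relationship of depth with poor outcome was confirmed" as evidence that this trial means to enrol cardiac patients. It describes an earlier trial and says nothing about eligibility here.

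**Conclusion.** The point holds in a limited form. As written, 1(a)(iv) together with the eligibility criteria would count an enrolled bypass patient with a recorded qualifying troponin or CK-MB change as an MI because of the index operation. Nothing else in the protocol plainly prevents this.

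The result would be higher MI and composite rates in both arms and a diluted relative effect. How large this is cannot be read from the protocol. The table rests wholly on assumed MI rates and bypass shares, and on counting all bypass patients, so each row is the most that its share could produce under those rates. With no bypass patients the effect is nil. The primary outcome and its sample size are unaffected.

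The wording should be corrected because the change is small and it protects the MI comparison, the composite and the Cox model. It does not threaten the trial's main conclusion.

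**What to change.** State in section 10 whether coronary surgery is eligible.

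If it is, reword 1(a)(iv) along these lines: a coronary artery intervention after, and other than, the index operation. The index procedure then cannot be the qualifying feature. Endpoint 2 needs no change on this account.

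If coronary surgery is not meant to be enrolled, say so in the exclusion criteria.

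Re-check MI reports in any cardiac surgical patients already enrolled against the clarified wording.

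The cost is a short protocol and CRF wording change plus that re-check. The small downside is a slightly stricter MI rule in cardiac surgical patients.

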7. ABBREVIATIONS

ANZCA	Australian and New Zealand College of Anaesthetists
ASA	American Society of Anesthesiologists
BIS	Bispectral index
CRF	Case report form
DMC	Data monitoring committee
DVT	Deep vein thrombosis
ECG	Electrocardiogram
EEG	Electroencephalogram
GA	General anaesthesia
GCRP	Good clinical research practice
ICU	Intensive care unit
MAC	Minimum alveolar concentration (of a volatile anaesthetic)
MAP	Mean arterial pressure
mBPI	Modified brief pain inventory
MI	Myocardial infarction
MIBI	Technetium-99m with the ligand methoxyisobutylisonitrile scan
PE	Pulmonary embolus
QoR-15	Quality of recovery -15 item questionnaire
RCT	Randomised controlled trial
SD	Standard deviation
SR	Suppression Ratio (of EEG)
WHODAS	World Health Organisation disability assessment schedule 2.0, 12 item.

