8. AIM OF TRIAL

Recent observational studies have found an association between deep anaesthesia and increased post-operative mortality in elderly and infirm patients undergoing major surgery. It is unknown whether there is a causal relationship in this observation, which occurs at levels of anaesthetic depth that are within the normal range of practice. We are performing a large randomised trial of 'deep' versus 'light' anaesthesia to definitively answer the question of whether anaesthetic depth alters perioperative outcome. Elderly patients undergoing major surgery will be randomised to an anaesthetic targeting either BIS=35 or BIS=50 for the deep and light groups respectively. The primary outcome variable will be all-cause mortality at one year and secondary outcomes will be MI, cardiac arrest, PE, stroke, sepsis, surgical site infection, ICU stay, hospital stay, awareness, WHODAS score, persistent postoperative pain and cancer recurrence.

Primary hypothesis

Light general anaesthesia (BIS = 50) is associated with decreased all cause mortality compared with deep general anaesthesia (BIS = 35) one year after major surgery in elderly patients.

Secondary hypotheses

Light general anaesthesia (BIS = 50) is associated with decreased incidences of MI, cardiac arrest, PE, stroke, sepsis and surgical site infection compared with deep general anaesthesia (BIS = 35) at 30 days and one year after major surgery in elderly patients.

Light general anaesthesia (BIS = 50) is associated with decreased incidences of a composite endpoint of MI, cardiac arrest, PE and stroke compared with deep general anaesthesia (BIS = 35) at 30 days and one year after major surgery in elderly patients.

Light general anaesthesia (BIS = 50) is associated with decreased cancer recurrence compared with deep general anaesthesia (BIS = 35) one year after major surgery in elderly patients.

Light general anaesthesia (BIS=50) is associated with an increased incidence of persistent postoperative pain compared with deep anaesthesia (BIS=35) at 30 days and one year after surgery in elderly patients.

Light anaesthesia (BIS = 50) is associated with increased disability-free survival compared with deep general anaesthesia (BIS = 35) one year after major surgery in elderly patients.

Safety and quality hypotheses

Light general anaesthesia (BIS = 50) is associated with improved early quality of recovery compared with deep general anaesthesia (BIS = 35) after major surgery in elderly patients.

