23.2 QoR-15 Score

How have you been feeling in the last 24 hours ?

0 to 10 where 0 = none of the time (poor) and 10 = all of the time (excellent)

1	Able to breathe easy	None of the time											all of 10 the time
2	Been able to enjoy food												all of 10 the time
		the time	0	1	2	3	4	5	6	7	8	9	10 the time
3	Feeling rested	None of											all of 10 the time
		the time	0	1	2	3	4	5	6	7	8	9	10 the time
4	Have had a good sleep	None of											all of 10 the time
		the time	0	1	2	3	4	5	6	7	8	9	10 the time
5	Able to look after personal toilet and hygiene unaided	None of											all of
	hygiene unaided	the time	0	1	2	3	4	5	6	7	8	9	10 the time
6	Able to communicate with family or friends	None of											all of 10 the time
		the time	0	1	2	3	4	5	6	7	8	9	10 the time
7	Getting support from hospital doctors and nurses	None of											all of
	nurses	the time	0	1	2	3	4	5	6	7	8	9	10 the time
8	Able to return to work or usual home	None of											all of
	Able to return to work or usual home activities	the time	0	1	2	3	4	5	6	7	8	9	10 the time
9	Feeling comfortable and in control	None of											all of
		the time	0	1	2	3	4	5	6	7	8	9	all of 10 the time
10	Having a feeling of general well-being	None of											all of
		the time	0	1	2	3	4	5	6	7	8	9	10 the time

Have you had any of the following in the last 24 hours?

(0 to 10 where 0 = none of the time (excellent) and 10 = all of the time (poor))

11	Moderate pain all or nearly all of the	time	None of											all of
			the time	10	9	8	7	6	5	4	3	2	1	0 the time
12	Severe pain at any time		None of											all of 0 the time
			the time	10	9	8	7	6	5	4	3	2	1	0 the time
13	Nausea or vomiting		None of											all of
			the time	10	9	8	7	6	5	4	3	2	1	0 the time
14	Feeling worried or anxious		None of											all of
			the time	10	9	8	7	6	5	4	3	2	1	0 the time
15	Feeling sad or depressed		None of											all of
_			the time	10	9	8	7	6	5	4	3	2	1	0 the time

23.3 The World Health Organisation disability assessment schedule 2.0.

12 Item interviewer-administered version (self-administered and proxy-administered versions are also available)

SECTION 3: PREAMBLE

SAY TO RESPONDENT:

The interview is about difficulties people have because of health conditions. (HAND FLASHCARD #1 TO RESPONDENT). By health condition I mean diseases or illnesses, other health problems that may be short or long lasting, injuries, mental or emotional problems and problems with alcohol or drugs.

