I remind you to keep all of your health problems in mind as you answer the questions. When I ask you about difficulties in doing an activity think about (POINT TO FLASHCARD #1).

- Increased effort
- Discomfort or pain
- Slowness
- · Changes in the way you do the activity

(POINT TO FLASHCARD #1). When answering, I'd like you to think back over the last 30 days. I also would like you to answer these questions thinking about how much difficulty you have, on average over the past 30 days, while doing the activity as you usually do it.

(HAND FLASHCARD #2 TO RESPONDENT). Use this scale when responding. (READ SCALE ALOUD): None, mild, moderate, severe, extreme or cannot do.

(FLASHCARDS #1 AND #2 SHOULD REMAIN VISIBLE TO THE RESPONDENT THROUGHOUT THE INTERVIEW.)

Flashcard #1

Health Conditions:

[figure not shown]
- Diseases, illnesses or other health problems
- Injuries
- Mental or emotional problems
- Problems with alcohol
- Problems with drugs

Having difficulty with an activity means:

- Increased effort
- Discomfort or pain
- Slowness
- Changes in the way you do the activity

Think about the past 30 days only

Flashcard #2

SECTION 4. CORE QUESTIONS

H1	How do you rate your overall health in the past 30 days ?	Very good	Good	Moderate	Bad	Very Bad
	Read choices to respondent.	25		22 22		24

SHOW FLASHCARD #2 to participant In the last 30 days how much difficulty did you have in: Extreme Mild None Moderate Severe /Cannot Do **S1** Standing for long periods such as 2 3 4 5 30 minutes? 1 **S**2 Taking care of your household 1 2 3 4 5 responsibilities? **S**3 Learning a new task, for example, learning how to get to a new 1 2 3 4 5 place? **S**4 How much of a problem did you have joining in community activities (for example, festivities, 1 2 3 4 5 religious or other activities) in the same way as anyone else can? **S**5 How much have you been emotionally affected by your 1 2 3 4 5 health problems?

Continue to next page ...

In the last 30 days how much difficulty did you have in:

	, , , , , , , , , , , , , , , , , , , ,					
		None	Mild	Moderate	Severe	Extreme /Cannot Do
S6	Concentrating on doing something for ten minutes ?	1	2	3	4	5
S7	Walking a long distance such as a kilometre [or equivalent]?	1	2	3	4	5
S8	Washing your whole body?	1	2	3	4	5
S9	Getting dressed?	1	2	3	4	5
S10	Dealing with people you do not know ?	1	2	3	4	5
S11	Maintaining a friendship?	1	2	3	4	5

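### Secondary endpoint 11 defines new-onset disability as a fall in the WHODAS score, but on the protocol's own form a fall is an improvement

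*Protocol*

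**What the plan says.** Section 10 of the protocol, secondary endpoint 11, defines disability-free survival up to one year as "survival and freedom from new-onset disability, the latter defined as a 4-point reduction in the WHODAS score". It adds that the date on which new disability begins will be recorded. Endpoint 10 gives the assessment times: "WHODAS score: pre-operative, day 30 and 1 year". Section 8 attaches a directional hypothesis to the endpoint: light anaesthesia "is associated with increased disability-free survival compared with deep general anaesthesia" at one year.

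The instrument is identified in section 7 as the "World Health Organisation disability assessment schedule 2.0, 12 item". The form in Appendix 23.3 asks "how much difficulty did you have in" each activity. Its response scale is "None, mild, moderate, severe, extreme or cannot do", numbered 1 to 5 in that order on items S1 to S12.

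Appendix 23.2 prints the QoR-15. The instruction above its symptom items (11 to 15) says "0 = none of the time (excellent) and 10 = all of the time (poor". The response line on each of those items puts 10 beside none of the time and 0 beside all of the time.

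**The concern.** An endpoint meant to capture deterioration is written in terms of a score that falls when the patient gets better. If the definition is carried as printed into a derivation, the survivor component of disability-free survival is turned round: recovery becomes the event and decline does not. The endpoint has its own directional hypothesis, so an inverted component could weaken, remove or reverse the estimated effect. The definition could also affect data capture. Item scores can be re-derived at any time, but an onset date recorded under the wrong direction may not be recoverable.

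The QoR-15 mismatch is a separate and smaller matter on a different instrument. It bears on the early quality-of-recovery hypothesis in section 8.

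**Working it through.** The protocol gives no figure to reproduce here, because this is a definition. The check is of direction.

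**Inputs**
- Printed event: a 4-point reduction in WHODAS (section 10, endpoint 11), read as baseline − follow-up ≥ 4.
- Items: 12, each coded 1 (none) to 5 (extreme or cannot do), with no reversed item (Appendix 23.3).
- Total score: the protocol prints item codes but no formula. A simple sum is assumed, giving 12 × 1 = 12 to 12 × 5 = 60. Direction does not depend on this choice, because any total that increases with the items behaves the same way.

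**Printed rule against the opposite rule (follow-up − baseline ≥ 4)**

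| Baseline → follow-up | Change in condition | Event as printed | Event if an increase is required |
|---|---|---|---|
| 24 → 36 | worse | no | yes |
| 24 → 28 | worse | no | yes |
| 24 → 24 | none | no | no |
| 24 → 20 | better | yes | no |
| 36 → 24 | better | yes | no |
| 12 → 60 | best to worst | no | yes |
| 60 → 12 | worst to best | yes | no |

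**All possible pairs of totals**
- There are 60 − 12 + 1 = 49 possible totals, so 49 × 49 = 2,401 pairs.
- Pairs with a fall of 4 or more: the sum of (49 − d) for d = 4 to 48, which is 45 + 44 + … + 1 = 45 × 46 / 2 = 1,035.
- Pairs with a rise of 4 or more: 1,035 by symmetry.
- Pairs in both sets: 0.
- Pairs classed alike by both rules (change under 4 points): 2,401 − 2 × 1,035 = 331.

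These are counts of possible score pairs. They are not estimates of how many patients fall in each.

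**Floor.** A patient with a baseline of 12, 13, 14 or 15 cannot fall by 4 points. Under the printed rule the least disabled patients at entry could never become newly disabled.

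**Why the scale must be named.** On a 12–60 or 0–48 scale, 4 points is 4/48 = 8.3% of the span. If the total were rescaled to 0–100 (an assumption, as the protocol does not mention it), 4 points would be 4 × 48/100 = 1.92 points on the simple sum, about half the threshold.

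**QoR-15.** Five items × 10 = 50 points, out of 15 × 10 = 150. A patient with no symptoms scores 50 on items 11 to 15 by the printed lines and 0 by the instruction above them.

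**The case against.** The intended meaning is not in doubt. Endpoint 11 names the event as new disability, so a competent programmer would probably code a worsening, and the wrong word looks like a slip. Section 10 also says that outcome definitions follow two other trials, which makes literal programming less certain still. The endpoint is one of 13 secondary endpoints, and section 15 records that disability-free survival was considered as the primary outcome and rejected. Because the items are collected, the WHODAS change can be corrected without new assessments.

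Most of this stands, and it limits the consequence. It does not cure the text. The pointer to other trials reverses nothing that is shown, and the only WHODAS scale in the protocol runs against the definition. An analysis plan that used the opposite direction would be at odds with the protocol.

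Three stronger readings are tempting but unsupported:
- A reader might infer that the endpoint will be analysed backwards. The documents show only that it is written backwards; the inversion occurs if the wording is applied literally.
- A reader might want a percentage of survivors misclassified. The protocol gives no WHODAS change data, and the pilot tables in section 9 report none, so any percentage would be invented.
- A reader might infer that QoR-15 scores are corrupted. Each of items 11 to 15 carries its own end labels, so a patient who marks the labelled line scores correctly whatever the instruction says. Misscoring is possible but not inevitable.

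**Conclusion.** The point holds as an error of direction in a stated endpoint definition. It rests on the protocol alone: item codes that rise with difficulty, no reversal anywhere, and an event defined as a reduction. The conclusion on direction needs only that the total increases with the items; the 12–60 range is an inference from the item codes.

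Applied literally, every survivor who changes by 4 or more points in either direction is put in the wrong class. Deaths remain failures, and survivors who change by less than 4 points are disability-free under either direction. The primary endpoint and the sample size are untouched. A reversed treatment effect on this endpoint is possible under literal application, but its likelihood cannot be judged from the documents. Because the definition supports a directional secondary hypothesis and can be put right in one line, it should be corrected before any derivation relies on it.

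The QoR-15 point is a genuine contradiction within the form but minor, with at most 50 of 150 points at risk for a respondent or data-entry clerk who follows the instruction.

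**What to change.** 1. In section 10, endpoint 11, define new-onset disability as an increase of at least 4 points from the pre-operative WHODAS score.
2. State the total-score scale to which the 4 points apply, since Appendix 23.3 prints item codes but no total. A simple sum would run from 12 to 60.
3. Check the CRF, any onset dates already recorded and the analysis programs for direction.
4. Separately, in Appendix 23.2, align the instruction for QoR-15 items 11 to 15 with the printed response lines (10 for none of the time, 0 for all of the time), and check that entered data follow the lines.

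The cost is short text corrections and a check of CRF, data and programming. No further patients or assessments are needed. The one item that might not be fully recoverable is an onset date already recorded under the wrong direction, which is a reason to check it early.
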